### **5.16 Potential Benefit of the Study Device**

Proper use of the study device may provide reduction in pain and improved function with the concomitant improvement in quality of life and daily activities. However, participants in the

 CartiHeal	CLN0021-US-Investigational Plan A Post Approval Multicenter Open-label Randomized Controlled Trial of Agili-C™ vs. Surgical Standard of Care (SSOC) for the Treatment of Joint Surface Lesions of the Knee	Document Number: CLN-0000002 Document Version: 8.0 Effective Date: 08-Jun-2022 (GMT+2) Page 25 of 80
		CLN0021-US Rev. 8 March 29, 2022

study may experience no direct benefit, although the findings from the investigation may benefit future patients with similar conditions.

## **6.0 Response Measures**

### **6.1 Safety Measures**

Adverse events, including serious adverse events, reoperations and revisions, up to 60 months

### **6.2 Study Arms**

[figure not shown]
#### **6.2.1 SSOC Group**

In the SSOC group, due to variety of pathologies, two surgical options are available to provide ideal treatment options. As part of the enrollment process, all patients will undergo arthroscopy. Patients will be treated by MFX and/or Deb (Figure 3) as described in Section 7.3, the surgical technique is according to standard of practice. All symptomatic lesions in the joint should be treated.

#### **6.2.2 Agili-C™ Group**

Agili-C™ is intended to be implanted following arthroscopy via a mini-arthrotomy or arthrotomy approach, using the designated surgical tools and surgical technique described in Appendix 5. The size of the implant(s) will be determined according to the size of the lesion(s) by the investigator according to the following algorithm (Figure 5):

 CartiHeal	A Post Approval Multicenter Open-label Randomized Controlled Trial of Agili-C™ vs. Surgical Standard of Care (SSOC) for the Treatment of Joint Surface Lesions of the Knee	CLN0021-US Rev. 8 March 29, 2022
---	---	---

**Figure 5: Implant Size Algorithm**

### **6.2.3 Concomitant Procedures**

Non-lesion related concomitant procedures, such as synovectomy, partial meniscectomy, high tibial osteotomy (HTO) and loose body removal are allowed, however ligamentoplasty is not allowed as concomitant; applicable for both treatment groups.

In case an HTO is performed concomitantly, the type of procedure and fixation technique will be documented. Additionally, the amount of HTOs will be stratified between the treatment arms.

## **7.0 Study Methods and Procedure**

### **7.1 Introduction**

Prior to enrollment of any study subjects, the PIs will undergo Agili-C™ specific surgical training to familiarize themselves with the Agili-C™ implantation, as well as training on the

A Post Approval Multicenter Open-label

Randomized Controlled Trial of Agili-C™ vs.

Surgical Standard of Care (SSOC) for the  
Treatment of Joint Surface Lesions of the Knee

CLN0021-US

Rev. 8

March 29, 2022

use of the various PROs and scales and other specifics of the protocol. Weight bearing X-ray imaging will be performed according to protocol in Appendix 3.

During the course of the study, subjects will be instructed to report any unusual signs or symptoms to the PI (or designee), who will solicit and record information about Adverse Events and Serious Adverse Events (AEs/SAEs), concomitant medications, therapies, and treatments. All reported AEs/SAEs will be documented on the appropriate case report form.

## 7.2 Subject Entry Procedures

### 7.2.1 Informed Consent Form and Subject Privacy

The purpose, procedures, risks, benefits, and alternatives to study participation will be discussed with each potential subject who has a knee surface lesion. Prior to any study-related procedures, the subject must sign an IRB/EC approved ICF and HIPPA Form (if applicable). If any new relevant information becomes available, the Sponsor will provide an updated ICF and HIPAA forms for IRB review and approval. The subject should personally sign and date the ICF and HIPAA forms. Upon signing the Informed Consent Form and authorization forms, the subject is considered to be a consenting individual in the study and receives a Subject Number that will be used on all documentation for the subject throughout the study.

After signing the Informed Consent Form, the consenting individual can then proceed with the screening evaluation. Surgery (Visit 2) must be performed within 1-90 days of signing the Informed Consent Form. During this period, if the subject decides to withdraw consent, the subject will then be considered as a screen failure. This will be captured in the screening log as well as in the CRF End/Exit form.

 CartiHeal	CLN0021-US-Investigational Plan A Post Approval Multicenter Open-label Randomized Controlled Trial of Agili-C™ vs. Surgical Standard of Care (SSOC) for the Treatment of Joint Surface Lesions of the Knee	Document Number: CLN-0000002 Document Version: 8.0 Effective Date: 08-Jun-2022 (GMT+2) Page 28 of 80
		CLN0021-US Rev. 8 March 29, 2022

## 7.2.2 Withdrawal Criteria

The subject has the right to withdraw from the study at any time without consequences, as indicated in the Patient Informed Consent documentation.

## 7.3 Study Visits

### 7.3.1 Screening Visit (Visit 1)

Following signing an informed consent, as described in section 7.2.1, candidates will undergo Initial Screening that includes lesion(s) assessment according to MRI and X-ray (not more than 1 year old), clinical history, physical examination and Patient Reported Outcome (PRO). A standing X-ray will be sent off-site for Kellgren–Lawrence evaluation to exclude K/L grade 4. The PI will be informed regarding subject eligibility according to K/L grade.

#### Initial Screening Visit (Visit 1) Activities:

1. Sign Informed consent
2. Assign Patient Number
3. Perform clinical examination
4. Review standing X-ray (AP and lateral, NMT 1 year old)
5. Review MRI (NMT 1 year old)
6. Record Medical history
7. Determine initial eligibility according to available inclusion/exclusion criteria
8. The investigator will complete:
  - a. IKDC Knee Examination Form 2000
  - b. ICRS Knee History Registration
9. The patient will complete the following questionnaires:
  - a. KOOS subscales
  - b. Tegner score
  - c. SF-12 Health Survey (v2)

d. ICRS Cartilage Injury Standard Evaluation Form 2000

e. 2000 IKDC Subjective Knee Evaluation Form

10. Analgesic, anti-inflammatory and prescription medication recording

11. The patient's MRI and standing X-ray (AP and lateral) will be sent off-site for OA evaluation according to Kellgren-Lawrence (K/L) score. In case of K/L < 4 (e.g. not severe OA) and absence of clear exclusion criteria as seen on the baseline MRI the PI will be informed that the patient is eligible for the study and the patient will continue to Visit 2.

In case of bilateral symptomatic knees, it is recommended that the most symptomatic knee be chosen for treatment in the study, as long as the inclusion/exclusion criteria are met. In case of equally symptomatic knees, the Investigator and the subject will determine which knee will be treated in the study. The knee that does not enter the study can be treated according to general practice. If during Visit 2 (Final Screening/Procedure Visit (arthroscopy)), the knee chosen is found to not meet the inclusion/exclusion criteria, the patient will be determined to be intra-op ineligible and not be included in this study for both knees.

### **7.3.2 Final Screening/Procedure Visit (Visit 2)**

- Between 1 to 90 days after initial screening, subjects will undergo Final Screening (Visit 2) via arthroscopy. If found eligible, the subject will be enrolled into the study and randomized intra-operatively into either Agili-C™ or SSOC. Stratification will be performed based on K/L score performed off-site.
- For the SSOC group, lesion treatment will be determined according to subject's age, lesion size and K/L grade (Table 1) as per the control group selection algorithm (Figure 3).

## A Post Approval Multicenter Open-label

Randomized Controlled Trial of Agili-C™ vs.

Surgical Standard of Care (SSOC) for the  
Treatment of Joint Surface Lesions of the Knee

CLN0021-US

Rev. 8

March 29, 2022

**Table 1: SSOC Sequence of Selection Criteria**

Criteria	Initial Screening, at site (Visit 1)	X-ray evaluation, off-site (Visit 1)	Arthroscopy & Final Screening, at site (Visit 2)
Age	X		
K/L grade		X	
Lesion Size			X

**Final Screening/Procedure Visit (Visit 2) Activities:**

1. Review of inclusion/exclusion criteria
2. Arthroscopy
3. Final enrollment
4. Randomization
5. Treatment (Agili-C™/ SSOC)
6. Film implantation procedure
7. Analgesic, anti-inflammatory and prescription medication recording
8. Record AEs/SAEs
9. Complete surgery debriefing forms

**Arthroscopy Procedure**

The arthroscopy procedure will be conducted according to hospital practice. Once subjects have fulfilled all the inclusion and none of the exclusion criteria, they will be enrolled into the study and randomized. The arthroscopy procedure should be video recorded according to hospital practice and documented post-procedure by the PI or study team on the relevant CRF assessment forms. The following structures should be carefully assessed by visualization and palpation:

- Synovia
- Patellar surface
- Trochlea surface
- Medial and lateral condylar surface

A Post Approval Multicenter Open-label

Randomized Controlled Trial of Agili-C™ vs.

Surgical Standard of Care (SSOC) for the  
Treatment of Joint Surface Lesions of the Knee

CLN0021-US

Rev. 8

March 29, 2022

- Medial and lateral tibial surface
- Medial and lateral meniscus
- Cruciate ligaments

Additionally, each lesion, regardless if symptomatic or not and if treated or not, should be documented according to the following parameters: location, severity (ICRS grade) and size (maximum length and maximum width). A company representative will be allowed to participate in the arthroscopy and to film the implantation procedure.

#### **Post-Procedure Treatment**

Recommended treatment for both groups is per the recommended rehabilitation protocol, see Appendix 6.

#### **7.3.3 Two weeks post-procedure ± 1.5 week (Visit 3)**

1. Record Adverse events
2. Analgesic, anti-inflammatory and prescription medication recording
3. X-ray (AP and lateral)

#### **7.3.4 Three months post procedure visit ± 2 weeks (Visit 4)**

1. Analgesic, anti-inflammatory and prescription medication recording
2. Record AEs/SAEs
3. MRI will be performed at 3 months to an initial cohort of at least 25 patients per study groups to evaluate presence of cysts

#### **7.3.5 Six months post-procedure ± 12 weeks (Visit 5)**

1. Weight bearing X-ray (AP and lateral)
2. The investigator will complete the IKDC Knee Examination Form 2000
3. The patient will complete the following questionnaires, either on-site or off-site:
  - a. KOOS subscales

- b. Tegner score
- c. SF-12 Health Survey (v2)
- d. 2000 IKDC Subjective Knee Evaluation Form
- 4. Analgesic, anti-inflammatory and prescription medication recording, either on site or off-site
- 5. Record AEs/SAEs either on site or off-site
- 6. MRI will be performed at 6 months to an initial cohort of at least 25 patients per study groups to evaluate presence of cysts

### **7.3.6 Twelve months post-procedure ± 16 weeks (Visit 6)**

- 1. MRI according to CartiHeal protocol
- 2. Weight bearing X-ray (AP and lateral)
- 3. The investigator will complete the IKDC Knee Examination Form 2000
- 4. The patient will complete the following questionnaires, either on site or off-site:
  - a. KOOS subscales
  - b. Tegner score
  - c. SF-12 Health Survey (v2)
  - d. 2000 IKDC Subjective Knee Evaluation Form
- 5. Analgesic, anti-inflammatory and prescription medication recording, either on site or off-site
- 6. Record AEs/SAEs, either on site or off-site
- 7. Off-site Defect fill evaluation (per MRI)

### **7.3.7 18 months post-procedure ± 16 weeks (Visit 7)**

- 1. Weight bearing X-ray (AP and lateral)
- 2. The investigator will complete the IKDC Knee Examination Form 2000

3. The patient will complete the following questionnaires, either on site or off-site:
  - a. KOOS subscales
  - b. Tegner score
  - c. SF-12 Health Survey (v2)
  - d. 2000 IKDC Subjective Knee Evaluation Form
4. Analgesic, anti-inflammatory and prescription medication recording, either on site or off-site
5. Record AEs/SAEs, either on site or off-site

### **7.3.8 24 months\* post-procedure ± 16 weeks (Visit 8)**

1. MRI according to CartiHeal protocol
2. Weight bearing X-ray (AP and lateral)
3. The investigator will complete the IKDC Knee Examination Form 2000
4. The patient will complete the following questionnaires, either on site or off-site:
  - a. KOOS subscales
  - b. Tegner score
  - c. SF-12 Health Survey (v2)
  - d. 2000 IKDC Subjective Knee Evaluation Form
5. Analgesic, anti-inflammatory and prescription medication recording, either on site or off-site
6. Record AEs/SAEs, either on site or off-site
7. Off-site Defect fill evaluation (per MRI)

\*Subjects that underwent surgical intervention in the index knee (interarticular surgery) prior to the 24M follow up visit, will complete up to 24-months of follow-up visits. These Subjects will not be asked to continue the study beyond the 24M follow-up visit.

A Post Approval Multicenter Open-label

Randomized Controlled Trial of Agili-C™ vs.

Surgical Standard of Care (SSOC) for the  
Treatment of Joint Surface Lesions of the Knee

CLN0021-US

Rev. 8

March 29, 2022

### 7.3.9 Annual post 24 months visits ± 16 weeks (until patient reaches 60 months\*)

1. Weight bearing X-ray (AP and lateral)
2. The investigator will complete the IKDC Knee Examination Form 2000
3. The patient will complete the following questionnaires, either on site or off-site:
  - a. KOOS subscales
  - b. Tegner score
  - c. SF-12 Health Survey (v2)
  - d. 2000 IKDC Subjective Knee Evaluation Form
4. Knee and AE treatment related medication recording, either on site or off-site
5. Record AEs/SAEs, either on site or off-site
6. MRI – optional

\* Subjects that underwent surgical intervention in the index knee (interarticular surgery) after the 24M follow-up visit, will not perform additional follow-up visits, beyond the time of the event (unless additional visits are required to follow their medical condition).

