## According to PI decision

## 7.5 Unscheduled Visit

Each time the subject returns to the study site, the PI (or designee) will solicit and record information about AEs, Knee and AE treatment related medications and therapies. All applicable procedures should be performed including MRI and X-ray (according to PI's decision).

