### 7.5.2 Unscheduled Visit with Surgery

In case of a secondary procedure, the following should be performed:

1. Investigator completes the IKDC Knee Examination Form 2000 (optional)
2. ICRS cartilage repair assessment form (if applicable)
3. Record AEs/SAEs
4. Knee related and/or AE related medication recording
5. Tissue and/or implant removal and histology (if relevant)
6. Video recording of the procedure with images captured (if applicable)

A Post Approval Multicenter Open-label

Randomized Controlled Trial of Agili-C™ vs.

Surgical Standard of Care (SSOC) for the  
Treatment of Joint Surface Lesions of the Knee

CLN0021-US

Rev. 8

March 29, 2022

The study protocol does not require a tissue biopsy. If clinically required, the tissue should be sent to a central lab for histological assessment as determined by the Sponsor. The Sponsor should be notified in advance and a Sponsor's representative will be allowed to participate in the procedure and film it.

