## 10.2 Analysis Populations

### 10.2.1 Safety Set

The safety population will consist of all patients for whom treatment with either Agili-C™ or SSOC was performed.

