### 10.6.2 Subject Disposition

Subject disposition will be tabulated; the number of enrolled, treated, prematurely terminated, and completed subjects will be summarized separately according to treatment and by visit (where relevant). A list of dropouts will be prepared including treatment, reason for discontinuation and time of discontinuation.

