## **10.8 Safety**

Safety analyses will be conducted on the safety analysis set. All AEs, including all SAEs and device/procedure related events (including possibly and probably related), will be summarized and tabulated. In addition, the following will be monitored:

- Secondary surgery rate
- Conversion to major knee procedure, such total/partial knee arthroplasty (TKA) and osteotomies
- Overall Failure Rate

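### Subjects with index-knee surgery leave scheduled safety follow-up before Month 60, and Protocol 10.8 tabulates later events with no allowance for time at risk

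*Protocol*

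**What the plan says.** Section 6.1 of the Protocol, like the synopsis, gives the safety endpoint as "Adverse events, including serious adverse events, reoperations and revisions, up to 60 months". The synopsis also places long-term safety within the primary objective. At Months 36, 48 and 60 the sites record AEs and SAEs, on site or remotely (7.3.9, Table 2).

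Two footnotes take operated subjects out of those visits:

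- Surgery before the Month 24 visit (7.3.8): visits continue to Month 24, and then "These Subjects will not be asked to continue the study beyond the 24M follow-up visit".
- Surgery after it (7.3.9): subjects "will not perform additional follow-up visits, beyond the time of the event (unless additional visits are required to follow their medical condition".

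Outside the scheduled visits, 7.5 provides: "Each time the subject returns to the study site, the PI (or designee) will solicit and record information about AEs". Section 7.5.2 adds: "In case of a secondary procedure, the following should be performed", and its list includes AE recording. Section 7.1 asks subjects to report unusual symptoms while they are in the study. Sections 8.0 and 9.8.2 follow known AEs and SAEs until they resolve or stabilise.

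On the analysis side, 10.2.1 begins "The safety population will consist of all patients for whom treatment with either" and covers both arms. Section 10.8 plans tables of events on that set and monitors the secondary surgery rate, the overall failure rate and "Conversion to major knee procedure, such total/partial knee arthroplasty (TKA) and osteotomies". It names no denominator, censoring rule or time at risk. Section 10.6.2 tabulates disposition by treatment and visit and adds: "A list of dropouts will be prepared including treatment, reason for discontinuation and time of discontinuation". Section 10.6.1 promises a general assessment of dropout effects. The SAP was written for 24 months and reports AEs as a percentage of all subjects (9.6).

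**The concern.** The endpoint has a 60-month horizon, but collection stops earlier for a group defined by a knee event. Take a subject with an arthroscopy at Month 15 and an arthroplasty at Month 40 in another hospital. The arthroscopy is counted. The arthroplasty enters the data only if the site learns of it, while the subject stays in the denominator of all treated patients. Conversion is a separately monitored item in 10.8, so counting the arthroscopy as a secondary surgery does not cover it.

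At stake is the description of long-term safety, which is a stated aim of this study. No hypothesis test depends on it.

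**Working it through.** **1. A figure to reproduce.** The documents give none for safety ascertainment. The nearest planning figure is the power for the primary endpoint in 10.7.1 (120 and 59 subjects, SD 25, difference 13.9, one-sided 0.025). A pooled t-test reproduces the stated 93.5%, and this point does not touch it.

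**2. Scheduled collection lost.** Inputs: the footnotes of 7.3.8 and 7.3.9, and visits at Months 36, 48 and 60. With first index-knee surgery at month m, and visit windows ignored:

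| Month of surgery | Visits lost | Months without scheduled collection |
|---|---|---|
| before 24 | 3 of 3 | 60 - 24 = 36 |
| 24 to under 36 | 3 of 3 | 60 - m, from 36 down to just over 24 |
| 36 to under 48 | 2 of 3 | 60 - m, from 24 down to just over 12 |
| 48 to under 60 | 1 of 3 | 60 - m, from 12 down to just over 0 |

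**3. What the remaining routes capture.**

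- Self-report (7.1) applies during the study; for early surgery, 7.3.8 ends participation at Month 24.
- Follow-up of open events (8.0, 9.8.2) concerns events already recorded. A knee problem that stays open could reveal a later arthroplasty, but 9.8.2 also allows some events to be closed as ongoing.
- Medically required visits are kept in 7.3.9 but not mentioned in 7.3.8.
- Sections 7.5 and 7.5.2 need the subject to return or the site to know of the procedure. The Protocol does not say whether they still apply after exit under 7.3.8.

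None of these is a scheduled contact that asks about new events.

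**4. Which outputs are exposed.**

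- Not exposed: any first reoperation, including an arthroplasty as first surgery, because the subject is still in scheduled follow-up until then. The same holds for per-subject failure and secondary-surgery rates, which the first event settles. Efficacy is also safe, because 10.4 sets failures' scores to baseline. Failures by injection alone do not trigger the exit rules.
- Exposed: conversion after an earlier surgery, second and later reoperations, and new AEs/SAEs after exit.

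**5. Effect on a crude percentage.** Let N be the treated subjects in an arm, E those with the event by Month 60, and U those whose event came after exit and was never learned of. The table shows (E - U)/N instead of E/N, so it is too low by U/N and never too high on this account. U depends on the share operated on, the later event rate and the share captured. The documents give none of these. The 15% failure rate in SAP Section 8 cannot stand in, because it is a 24-month planning value and includes injections. The error in the arm difference is the difference of the two U/N terms, and its sign is unknown.

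**6. Denominator.** The synopsis and 5.10 describe up to 251 pivotal-study subjects who remain in follow-up. Read strictly, that leaves out subjects who exit at Month 24 after early surgery. Section 10.2.1 takes all treated patients. The two readings give different conversion rates.

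**7. Timing.** Section 11.0 expects follow-up of all subjects to be complete in February 2025. Subtracting 36 months puts the last nominal Month 24 visit in February 2022; the 16-week window extends it to about June 2022. Rev. 8 is dated March 29, 2022. Most subjects operated on before Month 24 had therefore already reached their exit.

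**The case against.** The best defence is that the gap is narrower than it looks. Self-report, follow-up of open events and medically required visits all remain, and index-knee surgery may itself be an SAE that is followed. Disposition by visit and times of discontinuation are planned, so numbers under observation can largely be derived, and 10.6.1 promises to assess dropout effects. Subjects operated on early may lie outside the continuing cohort altogether. Everyone concerned is already counted as a failure, and an amendment has to pass ethics review across 22 centers.

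Much of this stands, and it lowers the severity. It does not close the gap. The routes miss unrelated new events and those after stabilisation. Section 10.8 does not use the disposition data. The cohort reading conflicts with 10.2.1 and would describe conversion only in subjects without early reoperation.

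A reader might infer that nothing is captured after exit, that reoperations in general are missed, or that the Month 60 efficacy result is weakened. The documents support none of these, for the reasons in steps 3 and 4 of the working.

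**Conclusion.** The point holds as a limited one. Under the plan as written, crude 60-month percentages for conversion after an earlier surgery, repeat surgery and late AEs/SAEs may be too low, and the denominator for subjects operated on before Month 24 is unsettled. The certain part is the schedule: one to three lost visits, and up to 36 of 60 months without scheduled collection per operated subject.

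It is tempting to put a number on the under-count or to say that it favours one arm. Neither is supported: reoperation, conversion and capture rates are all absent, and the direction would depend on which arm has more reoperations. The conclusion assumes only that some events after exit would not reach the site by the remaining routes. Severity is minor to moderate, confined to descriptive safety.

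**What to change.** 1. Amend 7.3.9: subjects operated on after Month 24 may stop questionnaires and imaging, but have a yearly off-site safety contact to Month 60 covering AEs/SAEs, further knee surgery and arthroplasty. Apply the same in 7.3.8 to anyone who has not yet exited. Off-site AE recording is already allowed in 7.3.9, and the SAP (10.5) describes telephone or web visits for this purpose.
2. State in 10.8 whether subjects operated on before Month 24 belong to the 60-month safety denominator.
3. In 10.8, report conversion and further surgery as cumulative incidence by arm, censored at the last safety contact, with numbers under observation at Months 24, 36, 48 and 60. State that censoring at exit after knee surgery is informative, so that post-exit events are incompletely ascertained.

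Cost: one amendment, one to three telephone contacts per subject operated on after Month 24 (up to three for any early-operated subject not yet out), and one extra table. Re-contacting subjects who have already left is optional. It is not cheap, and may need ethics approval and fresh consent, which the public documents do not settle. If it is not done, step 3 still prevents a crude percentage from being read as complete.
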